16.8 Data & Safety Monitoring

The principal investigator(s) and the study statistician will review the study at least twice a year to identify accrual, adverse event, and any endpoint problems that might be developing. The trial is monitored continually by the study team who are notified of every grade 4 and 5 event in real time. The Mayo Clinic Cancer Center (MCCC) Data Safety Monitoring Board (DSMB) is responsible for reviewing accrual and safety data for this trial at least twice a year, based on reports provided by the MCCC Statistical Office.

16.9a AE Stopping Rule

The stopping rule specified below is based on the knowledge available at study development. We note that the Adverse Event Stopping Rule may be adjusted in the event

of either (1) the study re-opening to accrual after any temporary suspension or (2) at any time during the conduct of the trial and in consideration of newly acquired information regarding the adverse event profile of the treatment(s) under investigation. The study team may also choose to suspend accrual because of unexpected adverse event profiles that have not crossed the specified rule below.

Accrual will be temporarily suspended to this study if at any time we observe events considered at least possibly related to study treatment (i.e., an adverse event with attribute specified as "possible", "probable", or "definite") that satisfy any of the following criteria across both cohorts combined.

- If at any time, 4 of the initial 10 treated patients or 40% or more of all patients (i.e. when accrual is greater than 10 patients) have experienced a grade 4 non-hematologic adverse event.
- If at any time, 2 patients have experienced a grade 5 adverse event (non -progressive disease).
- In addition, each grade 5 event will be reviewed on a case by case basis in a real time fashion to determine whether study accrual should be suspended. We may suspend accrual after just 1 grade 5 AE, if needed.

16.9b Accrual Monitoring Stopping Rule

Given the expected accrual rate is around 3 patients per month, it is expected that the study will take around 14 months to fully accrue. We plan to monitor the accrual continually and if we only end up accruing 5 patients or less in the first year (after study activation), we will consider stopping the trial for slow accrual.

16.9c Primary Endpoint Completion Time Estimation (For clinicaltrials.gov reporting)

The primary endpoint is the confirmed response rate, evaluated over the first year of treatment. The final analysis is expected to take place around 30 months after the study begins, so we expect that the primary endpoint completion time to be around 30 months after study activation.

16.9d Inclusion of Women and Minorities

This study will be available to all eligible patients, regardless of race, gender, or ethnic origin. There is no information currently available regarding differential effects of this regimen in subsets defined by race, gender, or ethnicity, and there is no reason to expect such differences to exist. Based on prior studies involving similar disease sites, we expect about 10% of patients will be classified as minorities by race and about 30% of patients to be women. Expected sizes of racial by gender subsets are shown in the following table:

Accrual Targets			
Ethnic Category	Sex/Gender		
	Females	Males	Total
Hispanic or Latino	0	0	0
Not Hispanic or Latino	13	28	41
Ethnic Category: Total of all subjects	13	28	41
Racial Category			

Ethnic Category	Accrual Targets		
	Sex/Gender		
	Females	Males	Total
American Indian or Alaskan Native	1	0	1
Asian	0	1	1
Black or African American	0	1	1
Native Hawaiian or other Pacific Islander	0	1	1
White	11	25	36
Racial Category: Total of all subjects	13	28	41

Ethnic Categories: **Hispanic or Latino** – a person of Cuban, Mexican, Puerto Rican, South or Central American, or other Spanish culture or origin, regardless of race. The term “Spanish origin” can also be used in addition to “Hispanic or Latino.”

Not Hispanic or Latino

Racial Categories: **American Indian or Alaskan Native** – a person having origins in any of the original peoples of North, Central, or South America, and who maintains tribal affiliations or community attachment.

Asian – a person having origins in any of the original peoples of the Far East, Southeast Asia, or the Indian subcontinent including, for example, Cambodia, China, India, Japan, Korea, Malaysia, Pakistan, the Philippine Islands, Thailand, and Vietnam. (Note: Individuals from the Philippine Islands have been recorded as Pacific Islanders in previous data collection strategies.)

Black or African American – a person having origins in any of the black racial groups of Africa. Terms such as “Haitian” or “Negro” can be used in addition to “Black or African American.”

Native Hawaiian or other Pacific Islander – a person having origins in any of the original peoples of Hawaii, Guam, Samoa, or other Pacific Islands.

White – a person having origins in any of the original peoples of Europe, the Middle East, or North Africa.

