16.6 Secondary endpoints

These endpoints include progression-free survival (PFS), overall survival (OS), and adverse events.

- Progression-free survival (PFS) is defined as the time from study entry to the first of either disease progression or death from any cause, where disease progression will be determined based on RECIST 1.1 criteria. PFS will be estimated using the Kaplan-Meier method.
- Overall survival (OS) is defined as the time from study entry to death from any cause. OS will be estimated using the Kaplan-Meier method.
- Adverse events: The maximum grade for each type of adverse event will be summarized using CTCAE version 4.03. The frequency and percentage of grade 3+ adverse events will be summarized.

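### The 40% stopping criterion in 16.9a counts grade 4 events only, so one pattern with a single related death (for example 3 grade 4 plus 1 fatal in the first 10) triggers no automatic suspension

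*Combined protocol and SAP*

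**What the plan says.** Section 16.9a (AE Stopping Rule) temporarily suspends accrual on "events considered at least possibly related to study treatment" that "satisfy any of the following criteria". Three bullets follow.

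- **Rate criterion.** Suspension if "4 of the initial 10 treated patients or 40% or more of all patients" (once accrual passes 10) "have experienced a grade 4 non-hematologic adverse event".
- **Two-death criterion.** "If at any time, 2 patients have experienced a grade 5 adverse event", progressive disease excluded.
- **Case review.** "each grade 5 event will be reviewed on a case by case basis in a real time fashion", to decide whether to suspend. Suspension after a single grade 5 event is allowed but not required.

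The preamble to 16.9a also lets the study team suspend for unexpected profiles that have not crossed the rule. Section 16.8 has the team notified of every grade 4 and 5 event in real time. The rule is said to apply across two cohorts, although the Trial Summary in Section 1.0 describes one treatment for all patients and Section 5.0 lists no grouping factor. No operating characteristics are given for the rule, and no toxicity rates by grade are assumed.

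**The concern.** The rate criterion names one grade rather than a threshold. Section 16.6 writes its adverse event summary as grade 3+, so the plan uses inclusive notation when it means it. Read literally, a patient whose only qualifying related event is fatal counts as treated but not as an event.

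This makes the rule non-monotone in severity. Four grade 4 patients among the first 10 make suspension mandatory. If one of the four instead has only a fatal event, no automatic criterion is met and suspension becomes a matter of judgement. A safety boundary should not become easier to satisfy when one outcome gets worse.

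**Working it through.** **Boundary.** The plan's own figure reproduces: 4/10 = 40%. For n > 10 the smallest count reaching 40% is ceil(0.40 × n): 6 at 15, 8 at 20, 12 at 30 and 17 at 41 (maximum accrual, Section 16.33).

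**Which patterns escape.** Let a be the number of patients with a qualifying grade 4 event and c the number whose only qualifying event is fatal. As written, suspension is automatic if a ≥ boundary or c ≥ 2. With inclusive wording it is automatic if a + c ≥ boundary or c ≥ 2. For 4 of the first 10 at grade 4 or worse:

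| (a, c) | Automatic as written? |
|---|---|
| (4, 0) | yes, rate criterion |
| (3, 1) | no |
| (2, 2), (1, 3), (0, 4) | yes, two-death criterion |

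At larger n the gap is again a single pattern, boundary minus one plus exactly one death: (5, 1) at 15, (7, 1) at 20, (11, 1) at 30, (16, 1) at 41. The shortfall is never more than one patient.

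**How often it arises.** The protocol gives no rates, so these are assumptions: p4 is the chance that a patient's worst qualifying event is grade 4 and p5 the chance that it is fatal. All fatal events are taken as non-hematologic.

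P(3, 1 in the first 10) = 10!/(3! 1! 6!) × p4³ × p5 × (1 − p4 − p5)⁶, with 10!/(3! 1! 6!) = 840.

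- 20%/2%: 840 × 0.2³ × 0.02 × 0.78⁶ = 3.0%
- 30%/2%: 840 × 0.3³ × 0.02 × 0.68⁶ = 4.5%
- 30%/3%: 840 × 0.3³ × 0.03 × 0.67⁶ = 6.2%

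**Effect over the whole trial.** Following both versions patient by patient to 41, with the two-death criterion active in both and the case review assumed never to suspend:

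| p4/p5 | Ever suspended, as written → inclusive | Inclusive wording acts earlier | Patients earlier, averaged over all trials |
|---|---|---|---|
| 5%/1% | 6.4% → 6.5% | – | – |
| 20%/2% | 32% → 34% | about 6% | 0.9 |
| 30%/2% | 59% → 62% | about 13% | 1.4 |
| 30%/3% | 67% → 71% | about 17% | 1.7 |

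Trials that never cross as written are counted as running to 41. Among affected trials only, the mean delay is about 16, 11 and 10 patients in the last three rows. That distribution is skewed: the median is 5 in both 30% scenarios. The all-trial average is the fairer summary.

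**The case against.** The best defence is that grade 5 already has its own, stricter treatment. Two related deaths suspend accrual at any point. Each single death must be reviewed in real time with power to suspend, and Section 10.331 requires deaths within 30 days of the last dose, and later related ones, to be reported within 24 hours. So a first death prompts a suspension decision after one patient, without waiting for the rate boundary. In every simulated trial where inclusive wording acts earlier, exactly one death is already on record and the review has been invoked. The calculated benefit therefore treats that safeguard as never suspending. Separate criteria for grade 4 and grade 5 are also a legitimate design. All of this stands, and it is why the point is minor.

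It does not remove the gap. The review is required but its outcome is open, and nothing tells reviewers to add the death to the grade 4 count.

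Two stronger readings are tempting, and the documents support neither.

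- A reader might infer that accrual can continue whenever 4 of 10 patients have grade 4 or worse toxicity, or that related deaths go unmonitored. Only the (3, 1) split escapes the automatic criteria, and that death must be reviewed.
- A reader might infer from Section 16.6 ("The maximum grade for each type of adverse event will be summarized using CTCAE version 4.03") that a death removes a patient already counted. That sentence governs the endpoint summary. The stopping rule counts patients who have ever had a grade 4 event, so someone with a qualifying grade 4 event who later dies remains in the count. The calculations ignore this overlap and to that extent overstate the effect.

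**Conclusion.** The concern holds in a narrow form. As worded, the rate criterion leaves one pattern, boundary minus one grade 4 patients plus exactly one related death, without mandatory suspension, although the same number of grade 4 patients would trigger it. The pattern needs a death with no earlier qualifying grade 4 event in that patient.

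The size is small: at most one patient short of the boundary, 0.9 to 1.7 patients in timing averaged over all trials, and a rise of 2 to 4 percentage points in the chance of ever suspending. These figures rest on assumed related rates of 20%/2% to 30%/3% and on a case review that never suspends. Nothing in the documents supports rates that high for this agent. At 5%/1% the difference is negligible. Minor severity: a wording correction to a safety boundary.

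**What to change.** In the first bullet of 16.9a, count patients with a *grade 4 or higher* non-hematologic adverse event, with progressive disease excluded as in the second bullet. Keep the two-death criterion and the case review unchanged. In the same edit delete the reference to two combined cohorts, since the trial has one. If the sponsor means deaths not to count toward the 40%, 16.9a should say so.

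The cost is one phrase. No new data are needed, because the team already receives every grade 4 and 5 event in real time. The downside is a slightly earlier temporary suspension after a related death. At the benign 5%/1% profile the chance of suspension moves only from 6.4% to 6.5%, so false alarms hardly increase.

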17.0 Pathology Considerations/Tissue Biospecimens

17.1 Tissue Biospecimen Submission

17.11 Summary Table of Tissue Biospecimens for This Protocol

Type of tissue biospecimen to submit	Mandatory or optional	When to submit	Reason for submission (background/methodology section)	Where to find specific details for biospecimen submission
Formalin-fixed paraffin-embedded (FFPE) tissue blocks with corresponding H&E OR 30 5- or 10-micron unstained slides with corresponding H&E) *Can be archival tissue	Mandatory	≤60 days after registration	Correlative studies (Section 17.3)	Section 17.2

If an institution is not able to provide the tissue, it does not cause the patient to be ineligible; however, the collection of these tissues is **strongly recommended**.

17.2 Paraffin Embedded Tissue Blocks/Slides (mandatory for research tissue)

17.21 Submit one formalin fixed paraffin-embedded (FFPE) tumor tissue block from the primary or recurrent/metastatic Small Bowel Adenocarcinoma. A corresponding H&E slide from the submitted block must be provided to permit quality assessment (QA) of tissue block.

17.22 The FFPE tissue block is preferred; however, if an institution is unable to provide a tissue block, cut 20 five-micron unstained slides and mount on charged glass slides and 10 ten-micron unstained slides mounted on uncharged slides. **Label the slides with the ACCRU patient ID number, accession number, and order of sections (i.e., 1-11). H&E stain the first cut slide (i.e., slide labeled 1). Please do not re-label over the original label.** For samples containing less than 7 square millimeters of tumor tissue, multiple sections should be mounted onto each slide to ensure that the appropriate amount of tumor tissue is available. Ideally, each slide must have a minimum of 75% tumor tissue on the slide to be deemed adequate for study. **Do not bake or place cover slips on the slides.**

17.23 The following materials below are mandatory (unless indicated otherwise) and required for shipment:

- Paraffin embedded tissue blocks with corresponding H&E (or 30 slides) per instructions in section 17.22
- Research Tissue Specimen Submission Form
- Surgical Pathology Report
- Operative Report-Optional

17.24 Ship all block/slide tissue specimens and accompanying materials to the following:

17.3 Study Methodology and Storage Information

17.31 Tissue microarray testing. FFPE tumor tissue blocks/slides will be collected in order to assess correlation of responses to treatment with PDL1 staining by immunohistochemistry (IHC). For tissue blocks received, tissue microarrays (TMAs) may be constructed and analyzed. For TMA constructions, the donor block remains intact except for 6 small (0.6mm) holes where the cores were taken. This process has minimal impact on the utility of the block for future clinical diagnostic needs. TMA construction and IHC stains will be performed in the Pathology Research Core Lab, Mayo Clinic Rochester. FISH analyses will be performed in the laboratory of [REDACTED].

17.32 Immunohistochemical analyses. The following protein biomarkers will be assessed by immunohistochemistry (IHC) on tumor samples obtained at baseline:

- MMR (MLH1, MSH2, MSH6, PMS2)
- PDL1 staining
- Lymphocyte-specific markers (*CD4, CD8, Bim, etc.*)

PD-L1 staining will be performed. All other IHC testing will be performed in the laboratory of [REDACTED]

[REDACTED] Analysis of all IHC slides, pathologic assessment will be performed by [REDACTED]

17.33 Nucleic acid analyses. PCR analysis for DNA mismatch repair deficiency/microsatellite insufficiency will be performed retroactively at the central lab on all tissue samples using the Promega MSI Analysis assay.

Genomic analyses (whole exome, RNA-Seq, etc.) may be performed at a future date for further characterization of total mutational burden, biomarkers, etc. DNA and/or RNA will be extracted and stored as stated in 17.54.

17.34 At the completion of the study, any unused/remaining material will be stored in the ACCRU Central Operations Office (Attn: Pathology Coordinator) for future research according to the patient consent permission (see Section 6.0). Potential future research may include immunohistochemistry (IHC) analyses, DNA extraction, and/or tissue microarray (TMA) construction to analyze predictive biomarkers, changes in expression pattern with therapy, and correlation with response and/or adverse events. For TMAs, the donor block remains intact except for 6 small (0.6mm) holes where the cores were taken. This process has minimal impact on the utility of the block for future clinical diagnostic needs. When a protocol is developed, it will be presented for IRB review and approval.

17.35 Banking of tumor tissue, according to the patient consent permission is for future research. As protocols are developed, they will be presented for ACCRU and IRB review and approval. (This collection is part of a general strategy of investigation for Mayo Clinic Cancer Center studies.)

17.36 The institutional pathologist will be notified by the ACCRU Operations Office (Pathology Coordinator) if the block may be depleted.

17.37 Blocks requested to accommodate individual patient management will be returned promptly upon request.

17.4 Return of Genetic Testing Research

Because the results generated by the genetic testing included in this section are not currently anticipated to have clinical relevance to the patient or their family members, the genetic results will not be disclosed to the patients or their physicians.

If, at any time, genetic results are obtained that may have clinical relevance, IRB review and approval will be sought regarding the most appropriate manner of disclosure and whether or not validation in a CLIA certified setting will be required. Sharing of research data with individual patients should only occur when data have been validated by multiple studies and testing has been done in CLIA-approved laboratories.

18.0 Records and Data Collection Procedures

All data must be entered by Remote Data Entry (RDE) and completed by qualified and authorized personnel. Access the RAVE RDE system through the iMedidata portal at [REDACTED]. All data on the CRF must reflect the corresponding source document. Please refer to the ACCRU website for instructions [REDACTED]. NOTE: All reports must be de-identified and labeled with the study number, ACCRU patient ID number and initials.

18.1 Submission Timetables

Initial Material(s) -

CRF	Active-Monitoring Phase (Compliance with Test Schedule Section 4.0)
On-Study	
Adverse Event Baseline	
Research Blood Submission - Baseline (see Section 14.0)	
Research Tissue Submission - Baseline (see Section 17.0)	≤2 weeks after registration
Concomitant Medication - Baseline	
Path Reporting (see Section 17.0) ¹	
RECIST Measurement – Baseline	
End of Active Treatment/Cancel Notification	Submit ≤2 weeks after registration if withdrawal/refusal occurs prior to beginning protocol therapy

1. Attach a copy of OP and path reports in RAVE using the Supporting Documentation Form for documentation of disease. This is in addition to the pathology material requirements for tissue submission (Section 17.0)

Test Schedule Material(s)

CRF	Active-Monitoring Phase (Compliance with Test Schedule Section 4.0)	
	At each evaluation during treatment	At end of treatment
Evaluation/Treatment	X ²	X
Adverse Event Form	X	X
RECIST Measurement	X ¹	X ¹
Research Blood Submission	X (see Section 14.0)	
Pathology Submission		
Concomitant Medication	X	X
End of Active Treatment/Cancel Notification Form		X
Deviation Form ³	X	
ADR/AER	At each occurrence (see Section 10.0)	

1. Attach a copy in RAVE for documentation of response or progression on the Supporting Documentation Form.
2. Complete at each evaluation during Active Treatment (see Section 4.0).
3. Submit only if applicable.

Follow-up Materia(s)

CRF	Event Monitoring Phase ¹				
	q. 3 months until PD	At PD	After PD q. 6 mos.	Death	New Primary
Event Monitoring Form	X ²	X ²	X	X	At each occurrence

1. If a patient is still alive 5 years after registration, no further follow-up is required.
2. Attach a copy in RAVE for documentation of progression on the Supporting Documentation Form.

19.0 Budget

- 19.1 Each site should review the test schedule (Section 4.0), taking into account local and regional coverage policies, to determine which items are standard of care and which are research at their site. Refer to the payment synopsis for funding provided per accrual for covering study costs, as well as any additional invoiceables that may be allowed.
- 19.2 Tests to be research funded:
 - 19.21 Mandatory blood samples done for research.
 - 19.22 Mandatory blood samples done for future research.
- 19.3 Other budget concerns: The study agent, pembrolizumab will be provided by Merck at no charge.

